8.2 SAFETY ASSESSMENTS

We do not anticipate adverse events associated with the intervention, and therefore we will not actively monitor for adverse events. However, if any adverse events occur among participants enrolled in the study, we will report them as required by the regulatory bodies.

8.3 ADVERSE EVENTS AND SERIOUS ADVERSE EVENTS

8.3.1 DEFINITION OF ADVERSE EVENTS

This protocol uses the definition of adverse event from 21 CFR 312.32 (a): any untoward medical occurrence associated with the use of an intervention in humans, ***whether or not considered intervention-related***.

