2.3 RISK/BENEFIT ASSESSMENT

2.3.1 KNOWNPOTENTIAL RISKS

Adapted from NIH Behavioral and Social Intervention Clinical Trial Protocol Template v3.0 - 20180827

There are no medical interventions associated with the study, therefore we anticipate no risk of serious physical harm to participating HCWs, adolescents or caregivers. In all HIV research studies there is a non-negligible risk of loss of confidentiality of HIV status or other medical information. There is also risk of emotional discomfort when responding to sensitive personal questions. HCWs who are trained in the DiSC intervention may have concerns about job loss if they perform poorly in implementing the stepped care approach. There is a possibility for social harm (depression, violence after disclosure, abandonment) related to routine HIV treatment and management during clinical encounters with routine providers during the course of the study. However, the possibility of this social harm would exist if this intervention were not conducted. There is a possibility that during a clinical encounter with the more intensive care steps, an ALHIV may be more comfortable disclosing that they are suffering from previously undiagnosed mental health problems such as depression. Any patients with potential mental health problems will be referred for psychosocial support at the facility or nearest referral hospital, according to standard HIV care and treatment guidelines for adolescents at that clinic.

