8.3.2 DEFINITION OF SERIOUS ADVERSE EVENTS

Serious adverse events will be defined as per the Division of AIDS (DAIDS) Table for grading the severity of adult and pediatric adverse events (grade 3-5 events).

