8.4.1 DEFINITION OF UNANTICIPATED PROBLEMS

This protocol uses the definition of Unanticipated Problems as defined by the Office for Human Research Protections (OHRP). OHRP considers unanticipated problems involving risks to participants or others to include, in general, any incident, experience, or outcome that meets **all** of the following criteria:

- Unexpected in terms of nature, severity, or frequency given (a) the research procedures that are described in the protocol-related documents, such as the Institutional Review Board (IRB)-approved research protocol and informed consent document; and (b) the characteristics of the participant population being studied;
- Related or possibly related to participation in the research (“possibly related” means there is a reasonable possibility that the incident, experience, or outcome may have been caused by the procedures involved in the research); and
- Suggests that the research places participants or others at a greater risk of harm (including physical, psychological, economic, or social harm) than was previously known or recognized.

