	Overall	Control	Intervention	Intervention vs. control
	Count (proportion) / Median (IQR)			^c RR (95% CI)
Per participant Number of viral load assays				
Over all participants Number of viral load assays Number of non-suppression results (%)				
Differentiated care: long-interval visits scheduled				
	Overall	Control	Intervention	Intervention vs. control
	Count (proportion) / Median (IQR)			^c RR (95% CI)
Per participant Number of scheduled visits				
Over all participants Number of scheduled visits Number of long-duration interval (%)				
Differentiated care: fast-track visits				
	Overall	Control	Intervention	Intervention vs. control

DiSC UH3 Statistical Analysis Plan (SAP)

	Count (proportion) / Median (IQR)			°RR (95% CI)
Per participant Number of visits with non-missing care model				
Over all participants Number of visits with non-missing care model Number of fast-track visits (%)				
Adherence				
	Overall	Control	Intervention	Intervention vs. control
	Count (proportion) / Median (IQR)			°RR (95% CI)
Per participant Number of intervals with good adherence				
Over all participants Number of intervals with good adherence Number of intervals with good adherence (%)				

^a Estimated by Poisson regression with robust errors

^b Estimated by Cox proportional hazards regression

^c Estimated by mixed-effects Poisson regression models with random effects for facility and participant and robust standard errors

*Models adjusted for any factors differing between arm with statistical significance at enrollment

Section 4. Missing data

While we will attempt to follow all participants at 12 months, we anticipate that EMR data and VL data may be incomplete for some participants might be a challenge due to participant loss to follow-up – either due to loss from care, or silent transfer to another facility. Due to the level of missingness we expect, we will not conduct any formal imputation.

Section 5. Safety monitoring

Adverse and severe adverse events, including social harms such as violence or breach of confidentiality, will be monitored as they arise, and unblinded results will be reviewed by the DSMB. The DSMB will make recommendations regarding any imbalances in safety outcomes.

SAE #	PTIDNO	Study arm	SAE description	Onset date	Duration (days / unresolved)	Onset since randomization (days)	Relatedness to study

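### The protocol limits adverse events to medical occurrences while the SAP promises the DSMB social harms, so those harms are not reliably captured

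*Protocol*

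**What the plan says.** **Foreseen risks.** Protocol 2.3.1 expects no serious physical harm. For HIV research it says that "there is a non-negligible risk of loss of confidentiality of HIV status or other medical information". It adds: "There is a possibility for social harm (depression, violence after disclosure, abandonment) related to routine HIV treatment and management", and remarks that this possibility would exist without the intervention.

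**Adverse events.** Protocol 8.3.1 covers "any untoward medical occurrence associated with the use of an intervention in humans", whether or not the event is thought related to the intervention. For seriousness, 8.3.2 says: "Serious adverse events will be defined as per the Division of AIDS (DAIDS) Table for grading the severity of adult and pediatric adverse events", meaning grades 3 to 5. Section 8.3.3.1 grades severity on the same table. Section 8.2 rules out active monitoring and promises to report whatever does occur as regulatory bodies require. Section 8.3.5 names the sponsor, PIs and ethics committee as recipients.

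**Unanticipated problems.** Protocol 8.4.1 requires three criteria together. The first is "Unexpected in terms of nature, severity, or frequency given (a) the research procedures that are described in the protocol-related documents", together with the participant population. The second is "Related or possibly related to participation in the research". The third is that the event suggests "greater risk of harm (including physical, psychological, economic, or social harm) than was previously known or recognized".

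**SAP.** Section 5 states: "Adverse and severe adverse events, including social harms such as violence or breach of confidentiality, will be monitored as they arise". Unblinded results go to the DSMB, which advises on imbalances. The display beneath has columns for SAE number, participant, arm, SAE description, onset, duration and relatedness. It has no line for a harm that is not an SAE.

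**The concern.** In a trial with no medical intervention, the foreseeable harms are mostly social. The SAP tells the DSMB to expect them as adverse events, but the protocol, which is what sites work from, uses a definition under which several of them are not adverse events. The DSMB can compare arms only on what sites record, so a listing with no social harms would be ambiguous: none may have happened, or the protocol may not have asked for them.

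The participants include minors, some of whom do not know their own HIV status (Protocol 2.3.3). The sample intervention steps in 6.1.1 include text reminders, home visits and treatment observed by a caregiver or family member. It is an inference, not a statement in the documents, that such steps could change exposure to disclosure in one arm. If they do, the between-arm comparison is what would show it. Case-by-case attribution is weak here because the intervention is delivered by routine staff at routine visits.

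**Working it through.** No arithmetic applies. The check takes each named harm through the protocol's two definitions and then looks for any other route to the DSMB.

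| Harm | Adverse event (8.3.1)? | Unanticipated problem (8.4.1, all three criteria)? |
|---|---|---|
| Confidentiality breach | Not a medical occurrence | 2.3.1 lists it as a research risk, so an ordinary case is expected in nature and hardly suggests a risk greater than recognised. A case unexpected in severity or frequency could qualify. |
| Violence after disclosure | Yes if injury results, with no relatedness needed; otherwise not plainly | From routine care: 2.3.1 foresees it and relatedness is doubtful. Caused by a study procedure: arguably unexpected, so it could qualify. |
| Abandonment | Not a medical occurrence | As for violence. |
| Depression | Yes, a medical condition | Not needed. |

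The gap is therefore the ordinary confidentiality breach, and abandonment or injury-free violence arising from routine care.

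Other places that might close it:

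1. Protocol 8.3.4 (assessment period), 8.3.8 (events of special interest) and 9.4.4 (safety analyses) are all marked NA.
2. Protocol 8.3.5 does not name the DSMB.
3. The UW criteria in 8.3.6 cover related events that are unexpected, or expected but more severe or frequent than expected. A related, expected event of ordinary severity is not listed.
4. Protocol 2.3.3 tells participants they can contact study staff about social harms. The stated response is counselling or referral, and no step for recording the harm as a safety event is given.
5. Protocol 10.1.10 treats noncompliance as a deviation, to be reported within 3 working days of identification and sent to the IRB/ERC. A staff-caused disclosure would probably fall here, but no onward route to the DSMB is stated.
6. Protocol 10.1.6 leaves the DSMB's data elements to its organisational meeting. The charter is not among the documents, and a charter can request only what sites have been told to collect.
7. The SAP Section 5 display is confined to SAEs. Protocol seriousness rests on DAIDS grades, and no rule says how a non-medical harm such as a breach would be graded.

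On monitoring, the SAP's phrase about events arising can be read as passive recording, which would be compatible with 8.2. Even on that reading, the documents differ on which events are to be recorded.

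**The case against.** The best opposing case is that the protocol has more safety nets than its adverse event definition suggests. Criterion three of 8.4.1 expressly includes psychological, economic and social harm, and criterion one can be met by unexpected severity or frequency as well as nature. Section 2.3.1 ties violence and abandonment to routine care, whereas 8.3.3.3 judges expectedness against risks described for study procedures. Violence or abandonment caused by a study procedure may therefore count as unexpected. Confidentiality duties in 2.3.3 and 10.1.3 make a staff-caused disclosure a probable deviation. The SAP itself classes social harms as adverse events, and the charter may ask for them.

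All of this stands, and it rules out three stronger readings. A reader might infer that the named harms fit neither definition. That is too absolute: depression and injury from violence can be adverse events, and some social harms can be unanticipated problems. A reader might infer that a site following the protocol would record nothing if a study procedure revealed an adolescent's status. The deviation route makes that unlikely. A reader might infer that the DSMB would certainly see no social harms. The documents do not establish that.

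What the objection does not supply is a rule under which an ordinary, foreseen social harm is collected and sent to the DSMB. The mention of social harm in criterion three does not help a harm that fails criterion one or two, and the deviation route ends at the IRB/ERC.

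**Conclusion.** The conflict between the documents is real. The protocol's definitions do not reliably capture the social harms that the SAP says the DSMB will review. Sites are not clearly required to report an ordinary confidentiality breach, or abandonment or injury-free violence from routine care, as safety events, so these may be under-reported.

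The size cannot be put as a count: the documents give no event rate, and the share caught by other routes is unknown. The effect is on interpretation, since a listing empty of social harms would not show their absence.

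The conclusion assumes that sites work from the protocol, and that no charter, manual of procedures or SOP outside these documents already sets a collection rule. If one does, the remaining defect is inconsistent wording. The point merits correction but does not touch the effectiveness analysis.

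**What to change.** Reconcile the two documents in four places.

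1. **Protocol 8.3.1.** Add social harms as reportable events: breach of confidentiality or unintended disclosure of HIV status, violence, abandonment, and other social or economic harm. State that they are reportable whether or not a medical occurrence results, and even when listed as a risk in 2.3.1. As with medical events, collect them regardless of relatedness and record relatedness separately.
2. **Protocol 8.2 and 8.3.5.** Align the monitoring statement with SAP Section 5, saying how staff are to record social harms they learn of, and name the DSMB as a recipient. Adding to 8.3.1 alone would not be enough, because 8.3.5 stops at the sponsor, PIs and ethics committee.
3. **Protocol 8.3.2 and 8.3.3.** State how non-medical harms are classified for severity and seriousness, since only DAIDS grading is given.
4. **SAP Section 5.** Widen the listing from SAEs to SAEs plus social harms, keep the arm column and add a type column.

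The cost is wording in both documents, one extra column and a few more reports to the ethics committees and the DSMB. No change to the design or the effectiveness analysis is needed.

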8.3.2 DEFINITION OF SERIOUS ADVERSE EVENTS

Serious adverse events will be defined as per the Division of AIDS (DAIDS) Table for grading the severity of adult and pediatric adverse events (grade 3-5 events).

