8.3.3 CLASSIFICATION OF AN ADVERSE EVENT

8.3.3.1 SEVERITY OF EVENT

We do not anticipate any significant adverse events to occur throughout this study. However, in the event that an adverse event occurs, participants will be given contact information for study team members and will contact study staff. Severity will be classified based on the DAIDS grading.

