8.3.6 SERIOUS ADVERSE EVENT REPORTING

In consultation with the PI, a trained member of the study team will be responsible for conducting an evaluation of a serious adverse event.

Reporting to Maseno University Ethics Review Committee (MUERC)

The investigator shall notify the secretariat by telephone ([name]) within twelve (12) hours of the event. In addition, the adverse event(s) noted during the conduct of a study or project must be reported to the MUERC via email ([contact]) within twenty-four (24) hours after the applicant becomes aware of the event. The investigator must submit a completed adverse event form alongside a summary of the event. The hard copies of the report must be forwarded to the MUERC Secretariat within three (3) working days of the initial notification.

Reporting to University of Washington IRB:

Adverse events that meet the following criteria must be reported to the UW Human subjects division

Adapted from NIH Behavioral and Social Intervention Clinical Trial Protocol Template v3.0 - 20180827

- a) AEs that were related to research procedures, serious, and unexpected (report immediately and within 10 business days)
- b) AEs that were related to research procedures and expected, but more severe or occurred at a greater frequency than expected (report immediately and within 10 business days)
- c) AEs that were related, non-serious, but unexpected (report annually)

Reporting to Study sponsor (NIH):
According to sponsor guidelines.

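### Protocol 8.3.2 defines a serious adverse event only by DAIDS severity grade, so seriousness becomes a cut-point on severity and can set the wrong reporting clock

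*Protocol*

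**What the plan says.** Protocol 8.3.1 takes its adverse event definition from a regulation: "This protocol uses the definition of adverse event from 21 CFR 312.32 (a"). For serious adverse events, 8.3.2 does not continue with that source. It says "Serious adverse events will be defined as per the Division of AIDS (DAIDS) Table for grading the severity" and then sets the threshold: "adult and pediatric adverse events (grade 3-5 events"). No outcome criterion is listed. Section 8.3.3.1 then applies the same instrument to severity: "Severity will be classified based on the DAIDS grading".

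Reporting follows in 8.3.6 and 8.4.2:

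- **MUERC, telephone.** Under the serious adverse event heading of 8.3.6, notice is due "within twelve (12) hours of the event".
- **MUERC, email.** In the same paragraph, "the adverse event(s) noted during the conduct of a study or project must be reported to the MUERC via email" within 24 hours of awareness. This sentence does not use the word *serious*.
- **UW.** There are three routes, all limited to events related to research procedures. Route (a) is "AEs that were related to research procedures, serious, and unexpected (report immediately and within 10 business days"). Route (b) covers expected events that prove more severe or more frequent than expected, on the same clock. Route (c) covers non-serious, unexpected events, which are reported annually.
- **Unanticipated problems (8.4.2).** The only timeline given is for those that are serious adverse events.

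SAP Section 5 refers to *severe* adverse events, but the listing below that text has SAE in its column headings.

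**The concern.** Severity describes how intense an event is. Seriousness describes its consequence, and it normally decides how fast an event is reported. Here one scale serves both, so the word *serious* in the reporting rules adds nothing beyond a grade of 3 or more. Yet 8.3.6 needs two ideas: route (a) turns on seriousness and route (b) on greater severity than expected.

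What is at stake is the speed and completeness of safety reporting, and what the DSMB sees in the SAE listing. The matter has some weight because the protocol (2.3.1) expects no serious physical harm and instead names loss of confidentiality, depression, violence after disclosure and abandonment. Neither document says how such harms are to be graded, or whether they can be serious adverse events. No endpoint, sample size or efficacy analysis depends on the definition.

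**Working it through.** There is no figure to reproduce. The check is to follow an event through the rules as written.

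**Step 1: is there another definition of seriousness?** Reading 8.3.1 to 8.4.3 of the protocol and Section 5 of the SAP, I find none. The regulatory citation in 8.3.1 covers adverse events only. The unanticipated-problem definition in 8.4.1 does not use seriousness. Grade 3-5 in 8.3.2 is therefore the only operative test.

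**Step 2: where does the label change what happens?** All three UW routes require relatedness. Route (b) applies to expected events. At UW, the label therefore matters only for related, unexpected events, where it separates route (a) from route (c). It also matters for the MUERC telephone notice, which sits under the SAE heading, and for the 8.4.2 timeline.

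**Step 3: follow two related, unexpected events whose grade and outcome disagree.**

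| | Grade 1-2, serious outcome (e.g. hospitalisation) | Grade 3, no serious outcome |
|---|---|---|
| Label under 8.3.2 | Not an SAE | SAE |
| UW (8.3.6) | Route (c): annual | Route (a): immediately and within 10 business days |
| MUERC telephone (8.3.6) | Not clearly required | 12 hours from the event |
| MUERC email (8.3.6) | Ambiguous: worded for adverse events, placed under the SAE heading | 24 hours from awareness |
| If also an unanticipated problem (8.4.2) | Reportable, but no deadline stated | MUERC at 12 and 24 hours; UW within 10 business days |

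If the second event were unrelated, it would still fall under the MUERC SAE notices but would enter no UW route. Over-reporting therefore falls mainly on MUERC.

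**Step 4: could a later reader of the data correct the label?** The SAP listing has columns for event number, participant, arm, description, onset date, duration, time since randomization and relatedness. It has none for grade or for the reason an event was called serious. The description may help for events that are listed, but an event excluded by the grade cut does not appear in the listing.

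**The case against.** The strongest reply is that the consequences are narrower than the definition suggests. Four parts of it stand.

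- **Several routes do not depend on seriousness.** Section 8.3.5 sends all unanticipated problems, including adverse events, to the sponsor, principal investigators and ethics committee. The MUERC email sentence is not limited to serious events. UW route (b) does not use the word. The unanticipated-problem definition in 8.4.1 expressly covers psychological, economic and social harm. These routes reduce the gap, but none of them defines seriousness or removes the move from route (a) to route (c).
- **Social harms have another path.** SAP Section 5 brings violence and breach of confidentiality to the DSMB without a grade limit. The protocol (2.3.1) also attributes the named social harms to routine care, and harms judged unrelated enter no UW route under any definition of seriousness.
- **Few events are likely.** There is no medical intervention, and 8.2 says adverse events are not actively monitored.
- **The usual outcome criteria appear nowhere in these documents.** They come from general practice. The internal inconsistency does not depend on them, but the proposed replacement does.

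A reader might infer more: that hospital admissions or social harms would in fact be graded below 3 and lost, or that any grade 3 laboratory value would become a serious adverse event and set off expedited reporting everywhere. The documents do not support this. The DAIDS table is not reproduced, so how it grades admissions, violence or laboratory values cannot be checked. The schedule of activities shows no safety laboratory tests, and grade alone does not trigger 10-day reporting to UW.

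**Conclusion.** The definition in 8.3.2 is wrong as written, and this is more than missing detail. It makes seriousness a threshold on the severity scale, while the reporting rules treat the two as different criteria. Where grade and outcome disagree, a related, unexpected low-grade event with a serious outcome drops from 10-business-day to annual reporting at UW, could miss the 12-hour MUERC call, and has no deadline in 8.4.2. In the other direction, a grade 3 event without a serious outcome triggers the MUERC notices.

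The conclusion rests on two assumptions: that staff apply 8.3.2 literally, and that grade and outcome can disagree for some events in this population. How often they would disagree cannot be estimated from the documents. With few events expected, the number affected is probably small. The point concerns the quality of safety reporting and leaves the trial's effectiveness results untouched. It should be corrected because the change is cheap and each of the few reports should be classified correctly.

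**What to change.** 1. Replace 8.3.2 with an outcome-based definition: death, life-threatening event, hospitalisation or its prolongation, persistent disability, congenital anomaly, or another medically important event.
2. Keep DAIDS grading in 8.3.3.1 for severity only.
3. State how serious social harms, such as violence or a breach of confidentiality, are classified and whether they can meet the definition.
4. Align the reporting text. In 8.3.6, say whether the MUERC email rule covers all adverse events or only serious ones. In 8.4.2, give a timeline for unanticipated problems that are not serious adverse events.
5. In SAP Section 5, change *severe* to *serious* where that is meant, and add columns for severity grade and seriousness criterion to the SAE listing.

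The cost is a few paragraphs of aligned wording across the two documents, two extra fields recorded for each listed event, and the usual ethics review of an amendment. No efficacy data collection, analysis or sample size changes.
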